6.17.3. Unplanned pregnancy

In the event that any subject becomes pregnant during the study, the pregnant subject will be withdrawn from the study. The optimal way to handle the implant will be reviewed on a case by case basis involving the investigator, obstetrician and the subject. No new data will be collected after withdrawal from the study. Data that have already been collected on

CLINICAL INVESTIGATION PLAN

withdrawn subjects will be retained and used for analysis, unless disallowed by national or local regulations.

6.17.4. Study Completion

All subjects will be evaluated at discharge from hospital, 4 weeks, 8, 16, 24, 36 and 52 weeks post implantation procedure. A subject's participation in the study will be considered complete after the 52-week visit.

7. RISK-BENEFIT ANALYSIS

7.1. Risks Assessment and Risk Mitigation

7.1.1. Risks Associated with ileostomy

Creation of a stoma is a well-established surgical technique and should only be carried out by a surgeon experienced in this procedure. The risks are well known and are reported in the published literature. They can be discussed according to time to onset. As a consequence of the complications listed below, the patient may require medical or surgical intervention, including re-operation.

Complications with onset within 30 days following ileostomy

- High output leading to dehydration/electrolyte abnormalities
- Ischemia/necrosis of the stoma
- Edema and venous congestion of stoma
- Retraction of stoma
- Technical complications
- Risk of recurrence in patients with Crohn's disease

Complications with onset after 30 days following ileostomy

- Peristomal skin complications
- Retraction of stoma
- Parastomal Hernia
- Mucocutaneous separation
- Peristomal pyoderma gangrenosum
- Stenosis
- Intestinal obstruction
- Technical complications
- Peristomal suppuration and fistula formation – Crohn's disease is associated with a higher risk.
- Recurrence of disease activity in patients with Crohn's disease

7.1.2. Risks Associated with the procedure of Implantation of the TIES® Port

Potential risks associated with implantation of the TIES® Port are described here, note that some of these complications are known complications of ileostomy. As a result of the complications listed below, the patient may require medical or surgical intervention, including re-operation and/or removal or replacement of the TIES® Port.

- Redness at the operation site
- Pain

CLINICAL INVESTIGATION PLAN

- Allergic reaction (including to medications, anaesthesia or device materials)
- Infection
- Device misplacement or displacement
- Enterocutaneous fistula
- Perforation of the intestine during insertion of ileum through implant
- Contamination of implant with intestinal content during surgery
- Narrow passage caused by irritated or swollen intestine
- Occlusion, sub-occlusion and constipation
- Parastomal/incisional hernias

7.1.3. Possible Risks Related to the TIES® Port, including Functional Risks

7.1.3.1

Titanium as a biocompatible material

The titanium used to manufacture the implant is a medically approved material that has been used in surgery for more than 30 years. Titanium is recognized to be non-allergenic. Various tests in line with regulatory standards have been performed during the development to ensure bio-compatibility of the TIES® Port with human tissue.

7.1.3.2

Potential risks post-surgery

It is important to maintain the TIES® Port in place during the healing period to facilitate tissue ingrowth into the implant in the abdominal wall and avoid applying any stress to the TIES® Port. Possible risks that may arise include:

- Insufficient ingrowth of soft tissue into the TIES® Port to ensure a leak-free system
- Leakage of intestinal liquid between the device and the skin due to:
 - Ileum retraction
 - Too early use of the TIES® Lid
 - Trauma
 - Other factors
 - External violence - skin or body injuries caused by the protruding part of the implant getting caught or by violent accidents

7.1.3.3

Actions required if ingrowth is insufficient

Should the system show incomplete ingrowth inside or outside or being harmed in a way or other over time, it should be “put to rest”. The usage of the TIES® Lid should be stopped for a few weeks to give the biological system time to adjust to the situation and come to a new balance; the ingrowth of the skin and the intestinal serosa and mucosa tends to adjust by itself.

7.1.4. Possible Risks Associated with the Post-Operative Care of the TIES® Port

All post-operative stoma care procedures are standard procedures and are not expected to add any additional risk. There are no additional risk-bearing procedures planned in the study (e.g. CT-Scan, X-rays).

Warnings and Precautions are included in the Surgical Procedure Manual and in the User Care Manual (see Appendix).

7.1.5. Possible Risks and Side Effects Associated with Medication

The patients may continue to take their usual medication as required. There is no additional medication required for the TIES® Port implantation procedure, other than that usually used to perform a common end ileostomy.

CLINICAL INVESTIGATION PLAN

There is no known incompatibility between the TIES® System and any medication.

7.1.6. Risks Mitigations

Risk mitigation in this study will be accomplished through the following actions:

- Clear definition of inclusion/exclusion criteria to ensure only appropriate subjects are enrolled, in line with contraindications listed in the Surgical Procedures Manual
- Ensuring that treatment and follow-up of the subject is consistent with current medical practices
- Selection of investigators who are experienced and skilled in performing ileostomy procedures
- Completion of training of site personnel by the Sponsor
- Performing all procedures in accordance with the Surgical Procedure Manual and User Care Manual
- Device training to the patient, per the User Care Manual
- Advise the patient on good care of the stoma and regular review by Stoma/ Research nurse
- Advise the patient on specific dietary measures to avoid excessive output
- Use of only soft catheter and soluble gel for intestinal emptying (flushing), to avoid occlusion, sub-occlusion and constipation
- Continuous safety review processes

7.1.7. Residual risks

There are known long-term risks associated with ileostomy. These include peristomal skin complications, retraction of stoma, incisional or parastomal hernia, mucocutaneous separation, intestinal obstruction, infection, fistula formation, or recurrence of the background disease. The presence of the implant is unlikely to alter the occurrence of these conditions and they can be treated using standard medical practice. It is expected that the study subjects will be followed up life-long in clinics specialised in care of stoma patients.

7.2. Benefit Assessment

7.2.1. Potential Benefits of the TIES® System

- Patient controlled continent ileostomy
- Fewer or no stoma bags needed
- Better quality of life (ability to travel, better social integration)
- Facilitated manipulation (clean and comfortable evacuation)
- Facilitated body hygiene
- No skin irritation resulting from stoma fixation device
- A leak-free system – “accidents” becoming a non-issue

7.2.1. Risks to Benefit Rationale

The product development and risk management activities for the TIES® System were performed while considering the essential requirements of the European Medical Device Directive (MDD) 93/42/EEC. Pre-clinical testing was performed using animal models and *in vitro* testing, before conducting clinical investigations in human subjects. OstomyCure AS has established manufacturing controls following the requirements of ISO 13485.

CLINICAL INVESTIGATION PLAN

The potential risks outlined above will be mitigated by proper patient selection, the attention given to the choice of investigational sites, the expertise of the investigators and surgeons, regular review by stoma/research nurse, and the training that will be provided to all involved study personnel, and to the patients.

It is noted that following any explantation/removal of the device, the patient can revert to use of ileostomy bags without any added risks.

The potential benefits of the system outweigh the potential risks, supporting use of the TIES® System in this study.

8. ADVERSE EVENT MANAGEMENT

Subjects will be carefully monitored during the study for possible adverse events (AEs) from the time the subject signs the Patient Informed Consent form to the completion of their participation in the study. Any AE observed will be fully investigated by the Investigator and classified in line with the definitions of the ISO14155:2011 as described below.

8.1. Definitions

Adverse Event (AE):

Any untoward medical occurrence, unintended disease or injury, or untoward clinical signs (including abnormal laboratory findings) in subjects, users or other persons, whether or not related to the investigational medical device

NOTE 1 This definition includes events related to the investigational medical device or the comparator.

NOTE 2 This definition includes events related to the procedures involved.

NOTE 3 For users or other persons, this definition is restricted to events related to investigational medical devices.

Treatment emergent adverse events are adverse events with onset at or following the implantation procedure for the purpose of this study.

Serious Adverse Event (SAE):

Adverse event that:

a) led to death,

b) led to a serious deterioration in the health of the subject, that either resulted in

- 1) a life-threatening illness or injury, or
- 2) a permanent impairment of a body structure or a body function, or
- 3) hospitalization or prolongation of existing hospitalization, or
- 4) medical or surgical intervention to prevent life-threatening illness or injury or permanent impairment to a body structure or a body function,

c) led to foetal distress, foetal death or a congenital abnormality or birth defect

NOTE Planned hospitalization for a pre-existing condition, or a procedure required by the Clinical Investigation Plan, without serious deterioration in health, is not considered a serious adverse event.

CLINICAL INVESTIGATION PLAN

Device Deficiency:

Inadequacy of an investigational medical device related to its identity, quality, durability, reliability, safety or performance. This may include malfunctions, use error, or inadequacy in the information supplied by the manufacturer.

Adverse Device Effect (ADE):

Adverse event related to the use of an investigational medical device

NOTE 1 This definition includes any adverse event resulting from insufficiencies or inadequacies in the instructions for use, the deployment, implantation, installation, operation, or any malfunction of the investigational medical device.

NOTE 2 This definition includes any event resulting from a use error or from intentional misuse of the investigational medical device.

Serious Adverse Device Effect (SADE):

Adverse device effect that has resulted in any of the consequences characteristic of a serious adverse event

Unanticipated Serious Adverse Device Effect (USADE):

Serious adverse device effect which by its nature, incidence, severity or outcome has not been identified in the current version of the risk analysis report.

NOTE Anticipated serious adverse device effect (ASADE) is an effect which by its nature, incidence, severity or outcome has been identified in the risk analysis report.

Use error:

Act or omission of an act that results in a different medical device response than intended by the manufacturer or expected by the user.

NOTE 1 Use error includes slips, lapses, and mistakes.

NOTE 2 An unexpected physiological response of the subject does not in itself constitute a use error.

Malfunction:

Failure of an investigational medical device to perform in accordance with its intended purpose when used in accordance with the instructions for use or CIP.

8.2. Event severity

Event severity is classified as follows:

Mild: awareness of a sign or symptom that does not interfere with the patient's usual activity or is transient, resolved without treatment and with no sequelae

Moderate: interferes with the patient's usual activity and/or requires symptomatic treatment

Severe: symptom(s) causing severe discomfort and significant impact on the patient's usual activity and requires treatment

CLINICAL INVESTIGATION PLAN

8.3. Causality relationship

The investigator will assess the causality of all adverse events in relation to the research, i.e., the relationship between the AE / SAE and the investigational treatment or any other study-related procedures.

Each SAE will be classified according to five different levels of causality:

1) Not related: relationship to the device or procedures can be excluded when:

- the event is not a known side effect of the product category the device belongs to or of similar devices and procedures;
- the event has no temporal relationship with the use of the investigational device or the procedures;
- the serious event does not follow a known response pattern to the medical device (if the response pattern is previously known) and is biologically implausible;
- the discontinuation of medical device application or the reduction of the level of activation/exposure - when clinically feasible – and reintroduction of its use (or increase of the level of activation/exposure), do not impact on the serious event;
- the event involves a body-site or an organ not expected to be affected by the device or procedure;
- the serious event can be attributed to another cause (e.g. an underlying or concurrent illness/ clinical condition, an effect of another device, drug, treatment or other risk factors);
- harms to the subject are not clearly due to use error;

- In order to establish the non-relatedness, not all the criteria listed above might be met at the same time, depending on the type of device/procedures and the serious event.

2) Unlikely: the relationship with the use of the device seems not relevant and/or the event can be reasonably explained by another cause, but additional information may be obtained.

3) Possible: the relationship with the use of the investigational device is weak but cannot be ruled out completely. Alternative causes are also possible (e.g. an underlying or concurrent illness/ clinical condition or/and an effect of another device, drug or treatment). Cases where relatedness cannot be assessed or no information has been obtained should also be classified as possible.

4) Probable: the relationship with the use of the investigational device seems relevant and/or the event cannot be reasonably explained by another cause, but additional information may be obtained.

5) Causal relationship: the serious event is associated with the investigational device or with procedures beyond reasonable doubt when:

- the event is a known side effect of the product category the device belongs to or of similar devices and procedures;
- the event has a temporal relationship with investigational device use/application or procedures;
- the event involves a body-site or organ that

CLINICAL INVESTIGATION PLAN

- the investigational device or procedures are applied to;
- the investigational device or procedures have an effect on;
- the serious event follows a known response pattern to the medical device (if the response pattern is previously known);
- the discontinuation of medical device application (or reduction of the level of activation/exposure) and reintroduction of its use (or increase of the level of activation/exposure), impact on the serious event (when clinically feasible);
- other possible causes (e.g. an underlying or concurrent illness/ clinical condition or/and an effect of another device, drug or treatment) have been adequately ruled out;
- harm to the subject is due to error in use;
- the event depends on a false result given by the investigational device used for diagnosis, when applicable

- In order to establish the relatedness, not all the criteria listed above might be met at the same time, depending on the type of device/procedures and the serious event.

8.4. Investigator Reporting Responsibilities

The investigator should report to the sponsor the following events, whether expected or not, in the corresponding CRF form, with the exception of AEs / SAEs detected before the patients has signed the patient consent form.

- AE
- SAE
- Device Deficiencies that did not but might have led to a SAE if:
 - o Suitable action has not been taken or
 - o Intervention had not been made or
 - o If circumstances had been less fortunate
- New findings/updated in relation to already reported events

If an AE / SAE is present at the beginning of study prior to the subject providing signed consent to participate in the study, only its worsening should be reported.

The investigator will document all AEs on the Adverse Event Form, including (at a minimum) a description of the event, date of onset, severity, relationship to the investigational device and/or procedure, required interventions, duration, and outcome. The investigator will monitor all AEs until they are resolved, determined to be a chronic condition or the subject is lost to follow-up. The investigator will report all AEs regardless of whether it is anticipated or unanticipated and regardless of classification, seriousness, intensity, outcome or causality.

All Serious Adverse Events including all device deficiencies that could have led to a SAE should be reported to the Sponsor within 24 hours of awareness of an event via the Adverse Event electronic Case Report Form in the study's electronic database, as that will trigger an immediate e-notification to the Sponsor and Devicia. All device deficiencies should also be reported without unjustified delay.

If the e-CRF is unavailable, notification to the sponsor can be made by email and the email address is [contact]

CLINICAL INVESTIGATION PLAN

The investigator must ensure that all additional relevant information (i.e., radiology reports, hospitalization reports indicating the SAE) that becomes available is also forwarded to the sponsor immediately after the initial notification and the information should be de-identified.

8.5. Reporting to Ethic Committee / Competent Authority

Depending on the local requirements or following agreement between both parties, the sponsor or the principal investigator will be responsible for performing safety reporting to the Ethics Committee according to the relevant local regulatory requirements.

Devicia will be responsible for reporting to the National Competent Authority according to national requirements and in line with MEDDEV 2.7/3.

The sponsor must report to the national Competent Authorities where the clinical investigation has commenced:

- a SAE which indicates an imminent risk of death, serious injury, or serious illness and that requires prompt remedial action for other patients/subjects, users or other persons¹¹ or a new finding to it: immediately, but not later than 2 calendar days after awareness by sponsor of a new reportable event or of new information in relation with an already reported event.
- any other reportable events as described in section 8.1 or a new finding/update to it: immediately, but not later than 7 calendar days following the date of awareness by the sponsor of the new reportable event or of new information in relation with an already reported event.

9. DATA SAFETY MONITORING BOARD

An independent committee comprised of experts in the field of gastroenterology or colorectal surgery will review all the safety and performance data on at least 2 occasions during the study:

- (1) The first review will take place after the first 5 subjects have been implanted and the fifth subject has been followed to 8 weeks. The purpose of the review of data to 8 weeks is to make recommendations if changes to the study design would be required. This meeting should be held about 4 weeks after the data becomes available.
- (2) The second review is planned after collection of 24-week results from the first 20 subjects to review if further modification to the collection of outcome measurements for performance assessment would be required.

In the event of reports of unexpected adverse events, an independent expert will review these unexpected adverse events and making assessment in regards of the seriousness and relationship to the device.

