10.2. Study design

This protocol plans for five interim data analyses during the course of this open study. The first two interim analyses are planned after collection of 8-week results from the first 5 and of 24-week results of the first 20 subjects, respectively, to review all available study data and to assess if there is a need to modify the study protocol including adjusting the collection of outcome measurements for performance assessment. The third, fourth and fifth interim analyses will be conducted when 50, 100 and 150 subjects, respectively, have completed 24 weeks follow-up in order to assess the primary and secondary 24-week safety and performance endpoints, make a preliminary assessment of the types of patient with high device acceptability, and consider whether some of the secondary study instruments (e.g. Quality of Life Questionnaires) can be dropped on the remaining patients to simplify follow-up and reduce burden on patients and clinical teams.

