10.10.2. Use of stoma bags

It should be noted that subjects will need to use stoma bags for at least the first 12 weeks until the TIES® Lid can be used regularly, and probably also during sleep after that period. Information on the continuous use of stoma bags during sleep based on recall will be recorded in subject's diaries at 16, 24, 36 and 52 weeks and will be presented using summary statistics.

CLINICAL INVESTIGATION PLAN

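### The first DSMB review rests on 8-week data, which hold no performance diary and little or no Lid exposure, and the next scheduled review waits for 24-week results on 20 subjects

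*Combined protocol and SAP*

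**What the plan says.** **Review schedule.** Section 9 says the committee "will review all the safety and performance data on at least 2 occasions during the study". For the first of these: "The first review will take place after the first 5 subjects have been implanted and the fifth subject has been followed to 8 weeks". Its purpose is stated as "The purpose of the review of data to 8 weeks is to make recommendations if changes to the study design would be required", and on timing, "This meeting should be held about 4 weeks after the data becomes available". Then "The second review is planned after collection of 24-week results from the first 20 subjects", to ask whether the collection of performance outcomes needs more change. No meeting is named between the two. Section 10.2 (repeated in the synopsis and section 3.1) has the first two interim analyses use all available data "to assess if there is a need to modify the study protocol including adjusting the collection of outcome measurements for performance assessment".

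**Lid and diary schedule.** Under the flow chart and section 6.9.2, bags are worn continuously until the 8-week visit. That visit judges whether healing is sufficient to start the Lid, and the start is put back by a week if tissue is trimmed. Section 10.10.2 adds that "subjects will need to use stoma bags for at least the first 12 weeks until the" Lid can be used regularly. Sections 4.1 and 10.4 take all performance data from diaries kept before the visits at 16, 24, 36 and 52 weeks. Section 7.1.3.2 lists as a risk "Leakage of intestinal liquid between the device and the skin due to" several causes, one of which is using the Lid too early.

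**The concern.** Closing the stoma with the Lid is what separates this device from a conventional ileostomy, and the primary endpoint (no leakage between Lid openings at 24 weeks) is defined by it. Earlier human experience is 11 patients and 13 implantation procedures (section 1.3). A staged early look by the DSMB is a sensible safeguard in that setting, but it is tied to the visit at which the Lid phase begins.

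Two things are at stake. First, the committee's early look covers surgery, healing and ingrowth but hardly touches the Lid phase. The next scheduled aggregate look comes only after 20 subjects have 24-week results, and no pause in enrolment is specified before then. Second, the first look is asked to help decide whether performance measurement needs changing, when the instrument that measures performance has not yet been used in data cut at week 8.

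**Working it through.** **Inputs.** Minimum 200 subjects (section 3.2); 48 months of enrolment, 12 months per subject and 5 years in total (synopsis); review triggers and the 4-week meeting lag (section 9); Lid first considered at week 8 (flow chart, 6.9.2); first diary at week 16, with a window of ±7 days (flow chart). The plan's own timeline reproduces: 48 + 12 = 60 months = 5 years. The plan does not state how many will be implanted at either review. The counts below assume that implantations accrue at the enrolment rate.

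**Accrual rate.** 200 / 48 = 4.17 per month. With 52.18 / 12 = 4.35 weeks per month this is 0.958 per week, or one subject every 1.04 weeks.

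**First review, even accrual.**

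| | Subject 5 | 4 | 3 | 2 | 1 |
|---|---|---|---|---|---|
| Weeks post-implant when subject 5 reaches week 8 | 8.0 | 9.0 | 10.1 | 11.1 | 12.2 |
| Weeks post-implant at the meeting, 4 weeks later | 12.0 | 13.0 | 14.1 | 15.1 | 16.2 |

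- If data are cut at week 8 for each subject, there are no diaries and no Lid time beyond the visit itself.
- If all data up to the trigger date are used, there are no diaries and at most 0 + 1.0 + 2.1 + 3.1 + 4.2 = 10.4 subject-weeks of possible Lid time.
- If all data up to the meeting are used, there are at most 10.4 + 5 × 4 = 30.4 subject-weeks of possible Lid time. Subject 1 is past week 16 and subject 2 is inside the visit window, so there are one or two diaries at most.
- Implanted: 5 + 8 × 0.958 = 12.7 at the trigger and 5 + 12 × 0.958 = 16.5 at the meeting.

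**Second review.** Implanted when the 20th subject reaches week 24 = 20 + 24 × weekly rate.

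| Accrual assumption | Implanted |
|---|---|
| Even, 48 months (0.958 per week) | 20 + 24 × 0.958 = 43.0 |
| Even, 36 months (1.278 per week) | 50.7 |
| Even, 60 months (0.767 per week) | 38.4 |
| Slow start over 48 months, cumulative ∝ t^1.5 | 38.0 |
| Slow start over 48 months, cumulative ∝ t² | 37.2 |
| Early rate 2.08 per month (0.479 per week) | 31.5 |
| Early rate 1 per month (0.230 per week) | 25.5 |

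The slow-start rows use N(t) = 200 (t/48)^k. For k = 2, the 20th subject enters at 48 × √0.1 = 15.18 months; adding 24 weeks (5.52 months) gives 200 × (20.70/48)² = 37.2. At even accrual over 48 months, the +14-day visit window moves 43 to 45, and a 4-week meeting lag (stated only for the first review) moves it to 47.

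**The same slow rates at the first review.** At 2.08 per month the five subjects are at 8.0, 10.1, 12.2, 14.3 and 16.3 weeks at the trigger, so one has reached week 16; with 4 weeks added, three have. At 1 per month they are at 8.0, 12.3, 16.7, 21.0 and 25.4 weeks, so three have; with 4 weeks added, four have. Slow early accrual therefore narrows the gap at both ends.

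**A look at week 16 of the fifth subject, even accrual.** Implanted: 5 + 16 × 0.958 = 20.3, or 24.2 at a meeting 4 weeks later. All five are then due to have completed a diary.

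**The case against.** **Safety oversight does not stop between the two reviews.** SAEs and device deficiencies that could have led to one go to the sponsor within 24 hours (8.4). Reportable events go to authorities within 2 or 7 days (8.5). An independent expert reviews unexpected adverse events (section 9), continuous safety review is listed as a mitigation (7.1.6), and the sponsor may suspend the study (11.6.1). This stands. A reader might infer that Lid-related harm goes unreviewed until the second DSMB meeting, and the documents do not support that. What is missing is narrower: a scheduled review of pooled Lid-phase data. The expert's remit is unexpected events, whereas leakage from early Lid use is already listed as a risk.

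**The first pack need not stop at week 8.** Sections 9 and 10.2 also speak of all data, and the meeting is about 4 weeks later. This stands too, so a claim that the first review holds no Lid exposure at all would go too far. But section 9 also describes the review as one of data to 8 weeks, and even the wider reading yields few diaries at the planned accrual rate.

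**The first look has other work, and a further meeting is already allowed.** Section 9 gives the first look a general design remit, and week 8 does assess the healing and ingrowth on which safe Lid start depends. Two occasions is a minimum. Lid use is not new in humans either: earlier implants stayed in place beyond 6 months in ten subjects, and three subjects past 60 months still request Lids (1.5). These points lower the urgency. They do not put a Lid-phase review on the calendar.

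**Bag period.** A reader might also see a contradiction between at least 8 weeks of bags (10.10.3) and at least 12 weeks (10.10.2). The first concerns continuous bag use and the second the time until regular Lid use, so the two are compatible and nothing needs reconciling.

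**Conclusion.** The point holds as a gap in the review schedule. Data cut at week 8 contain no performance diary and little or no Lid exposure, so they cannot inform the performance-measurement question that section 10.2 shares with this look. With all available data and the 4-week lag, even accrual adds some Lid-phase adverse events and at most one or two diaries. The next scheduled DSMB review falls at about 43 implanted under even accrual of 200 over 48 months, about 37 to 51 under the other enrolment patterns tried, and about 26 to 32 if early accrual is 1 to 2 per month. None of these counts is in the plan; they rest on the accrual assumptions shown and on no pause in enrolment. This is an inexpensive improvement to oversight and not a flaw in the primary analysis. It does not mean that Lid-related harm escapes individual reporting.

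**What to change.** - Keep the 8-week review, with its scope stated as surgical and ingrowth safety.
- In sections 9 and 10.2 (and the matching text in the synopsis and section 3.1), add one review by the same DSMB when the fifth subject has completed the 16-week visit. It should cover all data then available on all subjects: adverse events since Lid start, ingrowth, displacement and the first 72-hour diaries.
- Move the purpose of considering changes to performance measurement from the 8-week look to this one.

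The data are already collected at week 16, and section 9 already permits more than two meetings. The cost is one more data cut, one more meeting and the protocol wording. No visit, assessment or clinical rule changes.
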